### 13.4. Monitoring and Recording of Adverse Events

Adverse event data collection will begin after a subject signs the ICF and will continue until completion of the Safety Follow-up Visit (Visit 11). Any AE or SAE having an onset after the Safety Follow-up Visit will not be collected or reported unless the Investigator feels that the event may be related to the study drug.

Subjects will be instructed by the Investigator or designee to report the occurrence of any AE. All volunteered, elicited, and observed AEs are to be recorded on the AE eCRFs.

The Investigator will assess all AEs regarding any causal relationship to the study drug (see [Section 13.3](#)), the intensity (severity) of the event, action taken, and subject outcome.

The following criteria should be used to guide the assessment of intensity (severity):

- **Mild:** Causes awareness of sign or symptom, but is easily tolerated; does not interfere with usual activities
- **Moderate:** Causes discomfort enough to interfere with usual activities
- **Severe:** Is incapacitating; results in inability to work or perform usual activities

All AEs will be followed until resolution, until deemed stable by the Investigator, or until the subject is deemed by the Investigator to be lost to follow-up.

For clinical study safety reporting purposes, the most recent version of the Investigator's Brochure will be used as the reference document to designate event expectedness.

Withdrawal from the study as a result of an AE, and any therapeutic measures that are taken, shall be at the discretion of the Investigator. If a subject withdraws from the study for any reason, any ongoing AEs will be followed until resolution, until deemed stable by the Investigator, or until the subject is deemed by the Investigator to be lost to follow-up.

### 13.5. Reporting of Serious Adverse Events and Pregnancy

**All SAEs and pregnancies must be reported to Alkermes via Premier Research Group Limited immediately, within 24 hours of discovery, by emailing or faxing the report to the following:**

**Attention:** Safety Premier Medical Monitor

**US Email:** [contact]

**EU/Rest of the world (ROW) Email:** [contact]

**US Fax Number:** + 1 [contact]

**EU/ROW Fax Number:** [name]

The written report for SAEs should be submitted on the SAE form provided for this purpose. The SAE report must include the Investigator's opinion as to whether the event is study drug-related. If this relationship is determined to be possibly, probably, or definitely related to study drug, evidence to support this assessment must also be provided.

The written report for pregnancies in female subjects and in female partners of male subjects should be submitted on the Pregnancy Report Form provided for this purpose.

## 14. STATISTICS

### 14.1. Sample Size Considerations

Approximately 425 subjects will be randomized in order to have 400 subjects (200 per treatment group) in the efficacy population. Assuming the percent weight gain at Week 12 is 5% and 8.5% for ALKS 3831 and olanzapine groups, respectively, a common standard deviation of 8%, and a cumulative dropout rate of 35%, 200 subjects per treatment group (400 subjects in total) will provide at least 90% power to demonstrate a difference of ALKS 3831 relative to olanzapine at a two-sided significance level of 0.05.

### 14.2. General Statistical Methodology

The statistical analysis methods are described below. Additional details are provided in the Statistical Analysis Plan (SAP).

Baseline is defined as the last nonmissing values on or before the first dose of study drug in the double-blind Treatment Period.

In general, summary statistics (n, mean, standard deviation, median, minimum and maximum for continuous variables, and number [%] of subjects in each category for categorical variables) will be provided by treatment group for all variables.

Source data for the summary tables and statistical analyses will be presented as subject data listings.

All statistical tests and confidence intervals, unless stated otherwise, will be two-sided and will be set at  $\alpha=0.05$ .

#### 14.2.1. Study Populations

##### 14.2.1.1. Safety Population

The Safety Population, defined as all randomized subjects who receive at least one dose of study drug (ALKS 3831 or olanzapine), will be used in the safety analyses.

##### 14.2.1.2. Efficacy Population

The Efficacy Population (ie, full analysis set [FAS]), defined as all subjects in the Safety Population who have at least one postbaseline weight assessment, will be used in the efficacy analyses.

## 14.3. Demographics and Baseline Data

Demographics and baseline characteristics, such as gender, age, race, weight, BMI, and psychiatric history, will be summarized with descriptive statistics. If there are heterogeneities between study groups in any of the subject characteristics that are of clinical importance or could affect the treatment outcome, the impact of the imbalances will be investigated and, if necessary, appropriate adjustments will be made in the efficacy and safety analyses.

## 14.4. Efficacy Analyses

All efficacy analyses will be based on the FAS Population.

### Primary Endpoint

The primary endpoint is:

- Percent change from baseline in body weight at Week 12

The primary analysis will be carried out using an analysis of covariance (ANCOVA) method based multiple imputation (MI) for missing data. The model will include the treatment group and randomization strata as factors, and the baseline weight as the covariate. Sensitivity analyses will be carried out to explore the impact of missing data.

### Secondary Endpoints

The secondary endpoints are:

- Proportion of subjects with  $\geq 10\%$  weight gain at Week 12
- Proportion of subjects with  $\geq 7\%$  weight gain at Week 12
- Change from baseline in waist circumference at Week 12
- Change from baseline in CGI-S score within the ALKS 3831 Group at Week 12

For the categorical secondary endpoints of proportion of subjects with  $\geq 10\%$  and  $\geq 7\%$  weight gain at Week 12, the analyses will be carried out using a logistic regression model based on MI for missing data. The model will include the treatment group and randomization strata as factors, and the baseline weight as the covariate. For the change from baseline in waist circumference at Week 12, the analysis will be based on the ANCOVA method with MI for missing data, same as the primary analysis of the primary endpoint. For change from baseline in CGI-S within ALKS 3831 Group at Week 12, the analysis will be based on the mixed model with repeated measurements (MMRM). The model will include randomization strata, treatment, visit, and treatment-by-visit interaction term as factors; the baseline CGI-S value will be included as a covariate.

To control the overall Type I error rate, hierarchical testing will be performed in the following order: (1) percent change from baseline in body weight at Week 12, (2) proportion of subjects with  $\geq 10\%$  weight gain from baseline at Week 12, (3) proportion of subjects with  $\geq 7\%$  weight gain from baseline at Week 12, (4) change from baseline in waist circumference at Week 12, (5) change from baseline in CGI-S score within the ALKS 3831 Group at Week 12.

### Other Endpoints

Other endpoints are:

- Absolute change from baseline in body weight by visit
- Proportion of subjects with  $\geq 5$  cm increase from baseline in waist circumference at Week 12
- Body composition endpoints, as assessed by bioimpedance analysis, including

- Change from baseline in fat mass by visit
- Change from baseline in percent body fat by visit
- Change from baseline in fat mass index by visit
- Change from baseline in visceral adipose tissue by visit
- Change from baseline in lean mass by visit
- Change from baseline in fat free mass index by visit
- Change from baseline in total skeletal muscle mass by visit
- Percent and absolute change from baseline in fasting lipids (fasting triglycerides, LDL, HDL, total cholesterol), fasting glucose, HbA1c, and fasting insulin by visit
- Percent and absolute change from baseline in additional laboratory parameters including Apo B, Apo A1, Apo B/Apo A1, hs-CRP, IL-6, and TNF $\alpha$  by visit
- Change from baseline in CGI-S score (between and within treatment groups) by visit
- Change from baseline in CGI-S score (between and within treatment groups) by visit and by diagnosis
- CGI-I score by visit
- Change from baseline in IWQOL-Lite score by visit

Absolute change from baseline in body weight and all body composition endpoints will be analyzed using ANCOVA method with MI for missing data, same as the primary analysis of the primary endpoint.

The proportion of subjects with  $\geq 5$  cm increase from baseline in waist circumference at Week 12 will be analyzed by logistic regression model based on MI for missing data, in a similar fashion as the proportion of subjects with  $\geq 10\%$  weight gain.

The percent and absolute change from baseline in the laboratory parameters will be analyzed by MMRM model. The model will include randomization strata, treatment, visit, and treatment-by-visit interaction term as factors; the corresponding baseline value will be included as a covariate.

Change from baseline in CGI-S score between and within ALKS 3831 and olanzapine treatment groups (by visit, and by visit and by diagnosis) and change from baseline in IWQOL-Lite will be analyzed similarly by MMRM model.

CGI-I score, and CGI-I responder status ( $\leq 2$  versus  $> 2$ ) at each visit will be summarized by descriptive statistics.

Details of statistical methods will be listed in SAP.

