Proportion of subjects with shifts in blood pressure category by visit will also be analyzed based on each subject's by-visit assessment status using the logistic regression model described above. Shifts are defined as follows:

- Proportion of subjects shifting from Normal blood pressure at baseline to Stage 1 or Stage 2 Hypertension
- Proportion of subjects shifting from Normal or Elevated blood pressure at baseline to Stage 1 or Stage 2 Hypertension

The blood pressure categories will be defined as follows based on American Heart Association criteria:

- Normal: systolic and diastolic blood pressure of < 120 and $< 80 \text{ mmHg}$, respectively
- Elevated: systolic and diastolic blood pressure of ≥ 120 to ≤ 129 and $< 80 \text{ mmHg}$, respectively
- Stage 1: systolic blood pressure of ≥ 130 to $\leq 139 \text{ mmHg}$ or diastolic blood pressure of ≥ 80 to $\leq 89 \text{ mmHg}$

- Stage 2: systolic blood pressure of ≥ 140 mmHg or diastolic blood pressure of ≥ 90 mmHg.

The following laboratory parameters will be analyzed by MMRM model as described in [Section 3.8.3.4](#). The model will include treatment, visit, treatment-by-visit interaction, all randomization strata as categorical fixed effects; the baseline value will be included as the covariate. An unstructured variance-covariance matrix will be used.

- Percent and absolute change from baseline in fasting lipids (fasting triglycerides, LDL, HDL, total cholesterol), fasting glucose, HbA1c, fasting insulin, and HOMA-IR by visit
- Percent and absolute change from baseline in additional laboratory parameters including Apo B, Apo A1, Apo B/Apo A1, hs-CRP, IL-6 and TNFa by visit.

The proportion of subjects with metabolic syndrome at each visit will be analyzed by logistic regression model including treatment group and randomization strata as factors and baseline metabolic syndrome as covariate.

The proportion of subjects meeting each individual component criterion for metabolic syndrome (listed below) will be analyzed by visit using the same logistic regression model described above with the respective baseline value for each component as the covariate.

Additionally, a similar logistic regression model including treatment and randomization strata as factors will be used to analyze the proportion of subjects shifting from no metabolic syndrome at baseline to developing metabolic syndrome postbaseline. Data are based on observed values with no imputation for missing values.

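### No MMRM lets the baseline effect vary by visit, and the SAP's CGI-S model omits the baseline covariate that the protocol includes; correcting both would sharpen the Week 12 CGI-S estimate at almost no cost

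*Protocol*

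**What the plan says.** - **Protocol 14.4, Secondary Endpoints (CGI-S).** The MMRM has treatment, visit, their interaction and the strata, and "the baseline CGI-S value will be included as a covariate".
- **Protocol 14.4, Other Endpoints (laboratory).** "The model will include randomization strata, treatment, visit, and treatment-by-visit interaction term as factors; the corresponding baseline value will be included as a covariate". The between-arm and by-visit CGI-S analyses follow the same pattern, and "change from baseline in IWQOL-Lite will be analyzed similarly by MMRM model".
- **SAP 3.8.6 (laboratory).** "the baseline value will be included as the covariate". The weight MMRM in SAP 3.8.2.2, a sensitivity analysis of the average effect over visits, likewise has one baseline term.
- **SAP 3.8.3.4 (CGI-S, step 5 of the hierarchy).** The listed terms are treatment, visit, their interaction and the strata, with an unstructured covariance. Baseline CGI-S is not listed. SAP 3.8.6 refers the between-arm, by-visit and by-diagnosis CGI-S analyses and IWQOL-Lite back to this section, as applicable.

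No MMRM in either document has a baseline-by-visit interaction. For CGI-S the two documents disagree on whether baseline is in the model at all.

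**The concern.** CGI-S is rated at seven post-baseline visits (Weeks 1, 2, 4, 6, 8, 10 and 12). Some subjects enter soon after acute mania, some start as inpatients, and earlier medication may be tapered until Week 2. It is plausible that Week 1 severity tracks baseline more closely than Week 12 severity does. A single slope is then a compromise across visits. It fits Week 12 badly and leaves baseline variation in the Week 12 contrast. With no baseline term in a change-score model, the slope of the raw score on baseline is in effect fixed at 1, which is usually a worse fit.

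At stake is the width of the Week 12 confidence interval for the between-arm CGI-S difference. A reader would consult it when judging the expectation in protocol 5.3 that antipsychotic efficacy is similar in the two arms.

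**Working it through.** **1. The plan's own figure.** The only power statement concerns body weight. Inputs from protocol 14.1: "Assuming the percent weight gain at Week 12 is 5% and 8.5% for ALKS 3831 and olanzapine groups, respectively"; "a common standard deviation of 8" percent; 35% dropout; 200 per arm; "at a two-sided significance level of 0.05".

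- Completers per arm: 200 × 0.65 = 130. SE = 8 × √(2/130) = 0.992. 3.5/0.992 = 3.527. Power = Φ(3.527 − 1.960) = 94.1%.
- With 200 per arm: SE = 0.8 and power = Φ(4.375 − 1.960) = 99.2%.
- For 90%: 2 × 64 × (1.960 + 1.282)² / 3.5² = 109.8, so 110 per arm, and 110/0.65 gives 170.

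The statement "will provide at least 90% power" therefore holds as a floor. It does not bear on CGI-S, for which the documents give no SD, correlation or precision target.

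**2. Formula for the Week 12 loss (complete data).** Let b be the vector of true baseline slopes by visit, S the residual covariance, S12 its Week 12 variance, and b12 the Week 12 slope.

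- Common slope fitted by the MMRM: g = (1′S⁻¹b)/(1′S⁻¹1).
- Variance ratio, common slope to baseline-by-visit: 1 + Var(B)(b12 − g)²/S12.
- With no baseline term in a change-score model, replace g by 1.

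**3. Worked cases (assumed inputs, baseline SD 1).**

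- *Equal SDs, correlation 0.8 at Week 1 falling linearly by visit to 0.4, residual correlation exp(−gap/4 weeks).* g = 0.662 and S12 = 1 − 0.16 = 0.84. Common slope: 1 + 0.262²/0.84 = 1.082, so SE +4.0%. No baseline: 1 + 0.6²/0.84 = 1.429, so SE +19.5%.
- *SD rising to 1.4 at Week 12, correlations again 0.8 and 0.4.* b12 = 0.4 × 1.4 = 0.56, S12 = 1.96 × 0.84 = 1.646, g = 0.78. Common slope: 1 + 0.22²/1.646 = 1.029, so SE +1.4%. No baseline: 1 + 0.44²/1.646 = 1.118, so SE +5.7%.

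**4. Range with equal SDs.** For no baseline the ratio simplifies to 2/(1 + r12), where r12 is the Week 12 correlation.

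| Correlation, Week 1 / Week 12 | Common slope, SE excess | No baseline, SE excess |
|---|---|---|
| 0.5 / 0.4 | 0.1% to 0.2% | 19.5% |
| 0.6 / 0.4 | 0.4% to 0.8% | 19.5% |
| 0.7 / 0.3 | 2.0% to 3.8% | 24.0% |
| 0.8 / 0.4 | 4% to 5% | 19.5% |
| 0.8 / 0.2 | about 8% | 29.1% |

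At r12 = 0.5 the no-baseline excess is √1.333 − 1 = 15.5%, the lower end of the quoted range.

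More persistent residual correlation raises the common-slope loss. Pure exponential decay gives 9% to 14.5%. A 12-week residual scale gives 6.7% for 0.8/0.4 and 14.6% for 0.8/0.2. A rising SD lowers it: 0.8/0.2 falls to 5% to 6%.

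With the SD rising to 1.4, omitting baseline costs 1% to 13%. With a Week 12 SD 1.67 times baseline it costs 0% to 8%, and there a common slope can cost more than no baseline at all.

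**5. Simulation with about 35% dropout** (300 trials per setting, N = 400, seven visits, equal SDs). Model-based SE excess of the common slope: 0.2%, 0.9%, 4.6% and 8.7% for 0.5/0.4, 0.6/0.4, 0.8/0.4 and 0.8/0.2. Omitting baseline raised the empirical SE by 11% to 24%. Where slopes were equal or nearly so, the interaction raised the empirical SE by at most 0.7%, which is within simulation noise.

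**6. Step 5.** Assume a mean change of −1, SD 1.1 and 130 completers. SE = 1.1/√130 = 0.0965 and z = 10.4. An SE 9% larger gives 9.5; one 29% larger gives 8.0.

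**The case against.** A common-slope MMRM is a valid prespecified analysis of a randomized contrast, and the size of any gain cannot be fixed from these documents. That stands. Three stronger readings are tempting, and the documents support none of them.

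- **That baseline is known to predict Week 1 far better than Week 12.** No correlation is given. The mania criterion covers only bipolar subjects and dates the episode relative to Visit 1, with up to 30 days more before randomization. The slope also matters, not the correlation: a correlation falling from 0.75 to 0.60 leaves the slope flat if the SD rises by 25%, since 0.60 × 1.25 = 0.75.
- **That the Week 12 CGI-S interval is the trial's only randomized evidence on similar efficacy.** CGI-I by arm and discontinuation for lack of efficacy by arm are also randomized comparisons. CGI-S is the only one that is modelled. There is no equivalence margin, and SAP 3.8.6 limits such endpoints to an estimate, an interval and/or descriptive statistics.
- **That a confirmatory result is impaired.** The primary endpoint and steps 2 to 4 use multiple imputation with ANCOVA or logistic regression at Week 12. Step 5 is a within-arm change.

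The sentence quoted first also describes the laboratory models, which have only Weeks 2 and 12 after baseline; the gain there is smaller.

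Finally, the omission in SAP 3.8.3.4 may be a slip. The laboratory paragraph of SAP 3.8.6 cites that section and then adds a baseline covariate, which suggests one was intended. That supports correcting the text, because as written a programmer would fit CGI-S without baseline.

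**Conclusion.** The point holds as a precision improvement plus a documented conflict between protocol and SAP. It is not an error in a confirmatory result.

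A common slope costs about 0% to 9% of the Week 12 CGI-S standard error in most assumed settings (up to 1.09² = 1.19, or 19% in equivalent sample size), about 15% in extreme ones, and nothing if the slope is flat. The SAP's omission of baseline usually costs more: 15% to 29% with equal SDs and Week 12 correlations of 0.5 to 0.2, and 1% to 13% if the SD grows to 1.4 times baseline. All these figures rest on assumed correlations and SDs.

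A reader might also infer material bias in the treatment difference. The simulations do not establish that. In separate runs with severity-related dropout, the common slope shifted a within-arm Week 12 mean by at most 0.038 CGI-S points.

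**What to change.** 1. In SAP 3.8.3.4, restore baseline CGI-S as in protocol 14.4 and add baseline-by-visit.
2. Carry the same terms to the CGI-S and IWQOL-Lite MMRMs in protocol 14.4 and SAP 3.8.6. IWQOL-Lite has only Weeks 4 and 12 after baseline, so restoring baseline is the main gain there. The interaction is optional for the two-visit laboratory models.
3. State that LS means are evaluated at the overall mean baseline.

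For CGI-S the interaction adds six parameters with about 400 subjects and needs no new data. Because step 5 is in the testing hierarchy, make the change before unblinding. If the sponsor counts step 5 as a key secondary hypothesis, SAP section 5 calls for a protocol amendment. The primary analysis is untouched.

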## 14.5. Pharmacokinetic Analyses

Listings will be provided for concentrations of olanzapine, samidorphan, and metabolites of interest. Pharmacokinetic concentrations may be used in a subsequent population PK analysis conducted outside of this study.

## 14.6. Safety and Tolerability Analyses

All safety assessments will be summarized using descriptive statistics. All safety analyses will be based on observed data only, and no missing values will be imputed. Safety will be evaluated based on the occurrence of AEs, vital signs, results of clinical laboratory tests, and ECG findings. Reported AE terms will be coded using the MedDRA and will be summarized by preferred terms and system organ class categories.

Treatment-emergent AEs (TEAEs) are defined as AEs that occur or worsen after the first dose of study drug.

The summary tables will include the number and percentage of subjects with TEAEs by system organ class, and by preferred term within each system organ class. All SAEs, TEAEs leading to discontinuation, as well as additional categories of AEs, as defined in the SAP, will be summarized. The number and percentage of subjects with TEAEs will also be summarized for each study group by severity and by relationship to the study drug.

Observed values and change from Baseline in laboratory parameters, vital signs, and ECG parameters will be summarized by treatment group and study visit.

The number and percentage of subjects who have met potentially clinically significant (PCS) criteria at any post-Baseline visit will be summarized by treatment group for laboratory parameters, vital signs, and ECG parameters. Supporting listings will be provided.

The number and percentage of subjects with C-SSRS assessments of suicidal ideation and behavior will also be summarized.

Prior and concomitant medications will be summarized using the World Health Organization Anatomical Therapeutic Chemical (WHO-ATC) classification system. Listings will be provided for all concomitant medications.

## **15. DIRECT ACCESS TO SOURCE DATA/DOCUMENTS**

### **15.1. Study Monitoring**

Monitoring of the study site (including, but not limited to, reviewing eCRFs for accuracy and completeness) will be performed by an Alkermes Monitor or designee.

### **15.2. Audits and Inspections**

By signing the protocol, the Investigator agrees that, within local regulatory restrictions, and institutional and ethical considerations, authorized representatives of Alkermes, a regulatory authority, and/or an institutional review board (IRB)/independent ethics committee (IEC) may visit the site to perform audits or inspections, including the drug storage area, study drug stocks, drug accountability records, subject charts and source documents, and other records relative to study conduct. The purpose of an Alkermes audit or inspection is to systematically and independently examine all study-related activities and documents (eg, laboratory reports, x-rays, workbooks, subject medical records) to determine whether these activities were conducted, and whether data were recorded, analyzed, and accurately reported, according to the protocol, GCP guidelines of the International Council on Harmonisation of Technical Requirements for Registration of Pharmaceuticals for Human Use (ICH), and any applicable regulatory requirements.

The Investigator should contact Alkermes immediately if contacted by a regulatory agency regarding an inspection.

